# 5.5.3 Hypothesis

Ha The ophthalmic solution PRO-087 presents a safety and tolerability profile similar to comparators in healthy subjects

*Ho The ophthalmic solution PRO-087 presents a different safety and tolerability profile compared to comparators in healthy subjects.* 

# 5.6 Design and study plan

Clinical trial, phase I, controlled, parallel groups, double blind randomization, exploratory. 5.6.1 Discussion of the study design

The design of the study (clinical trial) is considered the highest quality standard in the data when it is sought to explore the effect of an intervention. The phase of pharmacological development (phase I) corresponds to the objective of the study which is to assess safety and tolerability, so that the intervention time is short and the sample size required is less than that of a clinical efficacy trial. The presence of parallel groups allows the comparison between the intervention groups on the outcome variables. Blinding and randomisation allow to reduce biases that are incurred with other designs, eg. Selection bias, evaluation bias, among others.

# 6. Material and methods. Participants, interventions and variables

# 6.1 Center of the study

The present study will be performed in ophthalmology offices duly equipped and registered for their proper functioning. According to the needs of the sponsor, these may be private or public, be attached to a hospital or clinic or be independent.

# 6.1.1 Organization of the center

Each study center will have a principal investigator (PI). The PI is the ophthalmology specialist in the clinical study.

The PI is responsible for forming a multidisciplinary research team to carry out the clinical study according to protocol, under its scientific guidance. It is the prerogative of the IP the design of the organization of its center and the selection of the personnel that will perform the functions. Nevertheless, the minimum organization of the research team requested by the sponsor requires the figure of sub-researcher, study coordinator and pharmacist. (See **Figure 1**)

Any person to whom the PI designates, under his / her responsibility, a part of the follow-up of the study (co-investigator, under-researcher, nurse, etc.) or a specific function of participation in the study (pharmacist, administrative assistant, study coordinator, etc.) should appear in the "Delegation of Responsibilities" format.

Figure 1 Minimum organization of the center

The "Delegation of Responsibilities" and the "Organizational Chart of the Center" must be delivered to the sponsor before the start of the study and updated if the members or their responsibilities are changed.

# 6.1.2 Documentation to be delivered to the sponsor

The PI must deliver to the sponsor, before the start of the study:

- Curriculum vitae updated, in Spanish, dated and signed (maximum 10 pages), of the IP and the staff that integrates its organizational chart of the center.

- Copy of IP academic certifications (degree certificate and specialty diploma in ophthalmology, federal professional certificates)

- Copy of academic certifications of the maximum degree obtained, from each one of the members of your research team, that cover their capacity to perform the delegated functions.

- Copy of operation notice or similar issued by corresponding regulatory entity (When applicable)

- Certificate of good clinical practice in force. If the issuing institution does not specify the validity period in the certificate, the date of issue of the certificate must not exceed one year

# 6.1.3 Closure of the center

The closing of the center will be carried out once the last visit of the last included subject previously agreed between the sponsor and the IP has been made. The closing process will be according to the internal operating procedures of the sponsor.

It is the prerogative of the sponsor to prematurely close a study center, it must inform the IP the reasons for the closure.

# 6.2 Eligibility criteria

# 6.2.1 Inclusion criteria

- Signed informed consent.
- Systemically and ophthalmologically healthy subjects evaluated during the clinical history.
- Age between 18 to 40 years.
- Both genders.
- Blood tests [complete blood count (BHc), three-element blood chemistry (QS) and liver function tests (PFH)] within normal parameters specified by the reference laboratory with a lower and upper margin of 10%.

- Vital signs within normal parameters.
- Visual ability 20/30 or better, in both eyes.
- Intraocular pressure ≥11 and ≤ 21 mmHg.

### 6.2.2 Exclusion criteria

#### 6.2.2.1 General criteria

- Subjects with a history of hypersensitivity to any of the components of the research products.
- Subject users of topical ophthalmic medications of any pharmacological group.
- Subject users of medication by any other route of administration.
- Pregnant or lactating women.
- Women without a history of hysterectomy, oophorectomy or hysterectomy, who do not ensure a hormonal contraceptive method or intrauterine device during the study period.
- Subjects with participation in clinical research studies 90 days prior to inclusion in the present study.
- Diagnosis of liver disease or triple the normal upper value of any of the following liver enzymes: aspartate transferase (AST), alanine transferase (ALT) or bilirubin.
- Inability to attend or answer the evaluations made in each of the visits.
- Positive tobacco use (specified as cigarette consumption regardless of quantity and frequency)
- Positive alcoholism (specified as the consumption of alcoholic beverages, regardless of quantity and frequency, during the study intervention period).
- Contact lens users.

#### 6.2.2.2 Medical and therapeutic criteria

#### 6.2.3 Elimination criteria

- Withdrawal of the consent letter under information.
- Presentation of serious adverse event.
- No tolerability or hypersensitivity to any of the compounds used during the tests (fluorescein, green lysine, tetracaine)
- No tolerability or hypersensitivity to any of the investigational drugs.
- Adherence <50% determined by the diary of the subject or by the weight of the bottle, of the established dose of the pharmacological intervention in any of the visits.

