#### Test product, dose and route of administration, lot number:

- PRO-087. Chondroitin sulfate 0.18% / 0.1% sodium hyaluronate, ophthalmic solution free of preservatives. Prepared by Sophia Laboratories, S.A. of C.V., Zapopan, Jalisco, Mexico.
  - Dosage: 1 drop 4 times a day during the waking period, both eyes
  - Route of administration: topical ophthalmic

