#### Duration of treatment: 10 days

#### Reference product, dose and route of administration, lot:

- 1. **Xyel Ofteno**®. Xantana gum 0.09% / Chondroitin sulfate 0.1% / preservative-free ophthalmic solution. Prepared by Sophia Laboratories, S.A. of C.V., Zapopan, Jalisco, Mexico.
  - a. Dosage: 1 drop 4 times a day during the waking period, both eyes
  - b. Route of administration: topical ophthalmic
- 2. **Systane Ultra®.** Polyethylene glycol 400 0.4%, propylene glycol 0.3%. Prepared by Alcon Laboratories, Inc.
  - a. Dosage: 1 drop 4 times a day during the waking period, both eyes
  - b. Route of administration: topical ophthalmic

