#### 6.3.2 Strategies to improve adherence and procedure to monitor adherence

1. Each visit the research subject will return the assigned bottle in order to evaluate the adherence by weight.

- 2. Direct questioning by the IP about the application of the intervention.
- 3. At the IP criteria, messages can be sent or reminder calls can be made.
- 4. Delivery of printed chronogram specifying the date of the visit and its activities
- 5. Journal of the subject.

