#### 6.3.2.1 Procedure to monitor adherence

Before delivering the medication to the research subject, the pharmacist must carry out the weighing of the bottles to be delivered. After the return of the medication by the subject will also carry out the weighing. Guidelines to follow for weighing:

- The pharmacist will use the scale provided by the sponsor
- Place the bottle in the center of the scale. You will get the result of the measurement.
- Remove the jar from the balance and put it back in, confirming that the measurement is the same. If it is different, it will weigh one more time and take the average of the 3 measurements
- Record the result in the log and the CRF provided by the sponsor

The adhesion will be calculated considering: the weight of the empty bottle, the weight of the drop, the weight of the bottle with the content, the calculation of the total of drops to be applied during the entire time of intervention and the total weight of the drops applied. The following simplified formula will be used:

$$Ad = \frac{\left(P_i - P_f\right)100}{P_T}$$

Where:

Ad = Adhesion

 $P_i$  = weight of the bottle delivered to the subject at the start

 $P_f$  = weight of the bottle returned by the subject

 $P_T$  = weight of the posology indicated for the intervention

$$P_T = (P_g)G$$

Where:

 $P_g$  = weight of the intervention drop, determined by the research and development department G = number of drops indicated for the intervention

Adherence will be estimated at each visit where the research subject returns the intervention. Only those bottles without apparent physical damage will be considered for the calculation. This result will allow the PI to determine if the subject continues in the study according to the stipulations of the elimination criteria.

The evaluation of the adherence by means of the diary of the subject will be carried out in the following way:

$$Ad = (A_r)100/A_i$$

*Ad* = Adherence

 $A_r$  = Registered applications

 $A_i$  = Applications indicated for the intervention

The final (overall) adhesion will be determined by the average of the adherence of each of the visits.

It will not be considered for the calculation of final adherence if the subject did not return the bottle in two subsequent visits.

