#### 6.3.4.1 Delivery and reception.

Delivery will be made in closed cardboard boxes by means of a courier service or directly by the sponsor's staff to the home of the research center according to the study plan.

The reception will be exclusively carried out by the research center team, including the researcher. You must check the good condition of the primary packaging (box). In the event that it shows alterations or defects in its integrity that from its judgment could have damaged the content, it should report it to the sponsor. If the package does not show significant defects, it will proceed to open it.

Inside you must locate the acknowledgment document and the logger (data logger) of temperature and humidity. You should check that the registered temperature and humidity comply with the specifications for transport and shelter (see section 6.3.4.2 Storage). Verify the content (interventions) with what is reported in the document. In case the document corresponds to the content, it will sign the receipt and send it to the sponsor. Otherwise, notify the sponsor.

In the study center, the personnel assigned by the PI will deliver the corresponding treatment to the subjects admitted, sufficient for the period to be covered. The delivery will be made in stages, medication will be delivered at the baseline visit, on visits 1 and 2. The center must register the medication delivered.

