#### 6.5.1 Procedures to be performed per visit.

#### 6.5.1.1 Scrutiny visit.

- Signature of informed consent: refers to the signing of the written informed consent document. See 10.3 Consent (assent)
- General and ophthalmological clinical history: refers to the technical, clinical and legal document in which the patient's health conditions, medical acts and other procedures performed on the patient are recorded chronologically. It includes the anamnesis and comprehensive ophthalmological exploration that allows to discern the patient's eligibility. If the patient is taken from the established consultation of the study center, he / she will be able to use the existing clinical history, only having to perform an update.
- Taking laboratory samples: see 6.4.3.12 Laboratory tests.
- Pregnancy test: see 6.4.3.11 Pregnancy test.
- Eligibility criteria: refers to the review by the IP, where it states that the subject can be included in the study by meeting the inclusion criteria and not meeting the exclusion criteria. See 6.2 Eligibility criteria
- Intraocular pressure: see 6.4.3.6 Intraocular pressure
- Visual ability: see 6.4.3.1 Visual capacity
- TRL: see 6.4.3.10 Rupture time of the tear film
- Epithelial defects (TF and TVL): see 6.4.3.4.1 Stains
- Eve signs and symptoms: see 6.4.3.4 Eye surface integrity: and 6.4.3.9 Ocular symptomatology
- Subsequent segment; see 6.4.3.7 Subsequent segment
- Vital signs: see 6.4.3.8 Vital signs

6.5.1.2 Basal Visit .

- Review of laboratory tests: refers to the review and analysis by the IP of the results of the BH, QS and PFH. See 6.4.3.12 Laboratory tests.
- Eligibility criteria: with the laboratory results, the subject's profile will be finalized for inclusion or not.
- Assignment: It refers to determining the intervention that the patient will follow during the study. It will be done according to section 7. Methods. Assignment of the intervention. This assignment will be made at the baseline visit (day 0) and will go along with the indication to start the treatment period the next day (day 1).
- Delivery of intervention: Refers to the delivery of the product under investigation to the patient of the study, by the research center. It will be done according to sections 6.3.1 Managed treatments and 6.3.4.1 Delivery and reception.

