- Those subjects who comply with an adherence greater than 60% will be included in the statistical analysis to meet the objective of the study. It was considered that from the minimum dose necessary to obtain a pharmacological effect and the presence of adverse events (exposure) is sufficient to fulfill the general objective of the design, according to the pharmacological characteristics of the product under investigation.

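### Adherence is judged visit by visit with no defined interval denominator, so on the nominal schedule a subject taking 35 of 40 applications can be eliminated while one taking 23 of 40 is analysed

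*Combined protocol and SAP*

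**What the plan says.** All references are to the combined protocol and SAP.

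- **Elimination (6.2.3).** A subject is eliminated for adherence under 50%, measured by the diary or "by the weight of the bottle, of the established dose of the pharmacological intervention in any of the visits".
- **Measurement (6.3.2 and 6.3.2.1).** "Each visit the research subject will return the assigned bottle in order to evaluate the adherence by weight". Fresh supply comes in stages: "medication will be delivered at the baseline visit, on visits 1 and 2" (6.3.4.1). Adherence is estimated at each return, and the investigator uses the result to decide whether the subject continues, under the elimination criteria. The denominators are the drops or applications prescribed for the intervention, and the text refers to the whole treatment time. No denominator for the interval between two visits is given.
- **Overall value (6.3.2.1).** "The final (overall) adhesion will be determined by the average of the adherence of each of the visits". No weighting is mentioned.
- **Analysis (8.3.1).** "Those subjects who comply with an adherence greater than 60% will be included in the statistical analysis". The section regards that exposure as enough for the general objective. It does not say whether the 60% refers to the overall value, or to diary or weight.
- **Population (8.3.3).** An analysis labelled intention-to-treat takes participants who completed Visits 1 and 2.
- **Adverse events (8.3.1).** These are reported for all eyes of randomised participants.

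**The concern.** Elimination and analysis use different limits on different bases. Elimination looks at one interval at a time, and the intervals are short and unequal, so a few missed drops in the shortest one can outweigh near-complete use elsewhere. The mean of visit percentages gives an interval of 8 applications the same weight as one of 20. Subjects can therefore be removed or kept in an order that does not follow their actual exposure.

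After baseline, goblet cell density, the comfort index and the laboratory samples are taken only at the final visit (6.4.4 and the schedule in 6.5). A subject eliminated at Visit 1 or 2 has no post-treatment value for these primary variables and, if eliminated at Visit 1, also falls outside the 8.3.3 population. Section 6.6.1 allows for few losses: 8 subjects needed and 10 enrolled per group.

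**Working it through.** **Inputs.** "Dosage: 1 drop 4 times a day during the waking period, both eyes" and "Duration of treatment: 10 days" (Summary) give 4 × 10 = 40 applications. Treatment starts on Day 1, the day after baseline (6.5.1.2). Visits fall on Days 3, 6 and 11, each ±1 day (6.5). The plan states no adherence figure to reproduce.

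**Literal denominator.** Applications due between visits, with visit-day doses taken after the visit, are 4 × 2 = 8, 4 × 3 = 12 and 4 × 5 = 20 (the last interval covers Days 6 to 10). Divided by all 40, a fully adherent subject scores 8/40 = 20%, 12/40 = 30% and 20/40 = 50%, mean 33.3%. The subject falls below 50% at Visit 1. The literal text cannot be what is meant, so the rest uses interval denominators of 8, 12 and 20.

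**Highest total that is still eliminated.** In an interval with n due (n even), the largest count below 50% is n/2 − 1. With everything else taken, the total is 40 − n/2 − 1.
- n = 8: 3/8 = 37.5%, total 35/40 = 87.5%.
- n = 12: total 33/40.
- n = 4: 1/4 = 25%, total 37/40 = 92.5%.

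The shortest interval governs, so the nominal figure is 35/40.

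**Lowest total that is analysed.** With every interval at exactly 50% (4/8, 6/12, 10/20) the total is 20 and the three percentages sum to 150. A mean above 60% needs a sum above 180. One extra application adds 12.5, 8.33 or 5 points in intervals 1, 2 and 3. Two extras add at most 25, which is too few. Three can suffice: 6/8, 7/12, 10/20 gives (75 + 58.3 + 50)/3 = 61.1%, total 23/40 = 57.5%.

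**Reverse error of the mean.** 4/8, 6/12, 16/20 gives (50 + 50 + 80)/3 = 60.0%, which is not above 60%, although the total is 26/40 = 65%.

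**Sensitivity to timing.** If visit-day doses come before the visit, the intervals are 12, 12 and 16 and the two limits become 33/40 and 24/40. Across all visit windows with 40 applications due, the highest eliminated total is 33 to 37 and the lowest analysed total 22 to 24.

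**Frequency (assumed inputs; the documents give none).** Applications taken in each interval are beta-binomial. Adherence is drawn separately for each interval, and r is the resulting correlation between applications in the same interval. Nominal schedule, probability that at least one interval is below 50%:

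| Expected adherence | r = 0 | r = 0.1 | r = 0.3 |
|---|---|---|---|
| 80% | 1.5% | 12% | 31% |
| 90% | 0.05% | 2.4% | 13% |

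At 80%, the probability of meeting the elimination rule although the total over the full course would exceed 60% is 1.4%, 8.5% and 19%. Among subjects not eliminated, the mean puts at most 0.6% of all subjects on a different side of 60% from the pooled ratio.

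**Loss allowance.** With X ~ Binomial(10, elimination probability), P(X ≥ 3) = 1 − P(X ≤ 2). At 80% adherence this is under 0.1%, about 11% and about 63% for r = 0, 0.1 and 0.3.

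**The case against.** Several points on the other side stand.

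- **The 37/40 case.** A reader might infer that a subject with 37 of 40 is routinely eliminated. On the nominal schedule this is impossible: three misses leave the worst interval at 5/8 = 62.5%. It needs an edge-of-window visit that leaves a single dosing day in an interval (Visit 1 on Day 2, or Visit 1 on Day 4 followed by Visit 2 on Day 5), with three of that day's four applications missed.
- **Contradictory limits.** A reader might infer that 50% and 60% contradict each other. They need not: one governs continuing and the other governs analysis, and a lower limit for the first can coexist with a higher one for the second. What is missing is a common basis.
- **Lost safety data.** Adverse events are counted in all randomised participants, and symptoms and diary are collected at Visit 1 itself. The loss concerns the later measurements.
- **Early misses as a sign of discomfort.** The documents do not say so, and 6.2.3 lists intolerance as a separate criterion. Informative loss is possible but not shown.
- **Size.** The frequencies rest on assumed adherence and correlation. Section 6.3.2 provides a diary, questioning, a printed schedule and optional reminders over 10 days in healthy volunteers, so adherence may be high and the rule seldom triggered.
- **A cumulative ratio alone.** At Visit 1 it equals the first-interval value, so 3/8 stays at 37.5%.

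None of this removes the undefined denominator or the inversion between exposure and inclusion.

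**Conclusion.** The point holds in a limited form. The adherence denominator must be defined, because the literal text eliminates fully adherent subjects. On the interval reading, the rules allow 35/40 to be eliminated while 23/40 is analysed (33/40 and 24/40 if visit-day doses come first). This takes the 60% in 8.3.1 to be the overall value of 6.3.2.1. The any-visit rule is the main problem, and the unweighted mean is a minor one.

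How many subjects are affected cannot be settled from the documents. It ranges from almost none (90% adherence, independent misses) to nearly a third (80%, correlation 0.3). In groups of 10 with a margin of 2, the upper part of that range matters for the Day 11 primary measurements. It is a change that should be made, not evidence that the trial cannot answer its question.

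**What to change.** 1. **6.3.2.1:** define adherence at each visit as total applications (or product weight) used divided by the total indicated to date, and overall adherence as total used divided by total indicated, not as a mean of visit percentages. State whether diary or weight decides. This corrects denominator and weighting, but does not by itself protect a subject with early misses at Visit 1.
2. **6.2.3, 8.3.1 and 8.3.3:** reconcile the three rules on who continues and who is analysed. The limit, and any rule on stopping treatment, are for the sponsor to decide.
3. **8.3.1 and 8.3.3:** still make the scheduled assessments of subjects below the adherence limit, include all randomised subjects with data in the main safety and tolerability analysis, and use the limit only to define a sensitivity set.

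The cost is wording in four sections and the remaining visits of the few subjects concerned; the same bottle weights and diaries are used. The downside is that a few less exposed subjects stay in the main analysis, which may slightly dilute differences between groups. The sensitivity set shows whether that matters.

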#### 6.2.4 Identification of the subject

The patients of the study will be identified by a number and the initials of their name.

The initials of the study subject will be obtained starting with the first letter of the name, followed by the first letter of the first surname and the first letter of the second surname, obtaining maximum three letters, in case the person has two names or a compound surname the first letter will always be used.

#### Example:

#### 1. [name]

Sophia Laboratories, S.A. of C.V.

- CONFIDENTIAL
- a. Initials: AMC
- 2. [name]
  - a. Initials: JDO

In the counting stage, the participant number will be assigned consecutively, using 3 consecutive digits. Once the subject has been selected, he will be assigned a number with which he will be identified throughout the study. Said code will be composed of eight numbers in the following order from left to right:

- Three digits of the molecule under study according to the denomination by the sponsor.
- Two digits corresponding to the research center number.
- Three digits of the number consecutive to its inclusion assigned to the research center.

Example:

